3.4.6 MRI staff

The MRI staff will be responsible for performing the MRI investigations according to the study MRI manual (separate document). Original data will be exported to the MIAC, c/o University Hospital Basel, Switzerland, and primary data will be stored at the study site.

3.4.7 Local neurologist/radiologist or neurologist with MRI expertise

The local neuroradiologist or a neurologist with MRI expertise will review the MRI images for safety purposes and provide access to the subject's MRI images and/or reports to the principal investigator / treating neurologist. Significant findings, which, in view of the local neuroradiologist, meet the definition of an AE must be assessed for seriousness, reported to the principal investigator / treating neurologist and recorded on the AE page of the eCRF. In the event of safety findings of potential clinical concern observed on the MRI scans at any visit during the study, the local neuroradiologist will conduct further examination, as per local standard practice, to rule out or confirm the diagnosis. This also applies to incidental findings with safety concerns that have been detected during central MRI reading at MIAC and communicated to the local radiologist.

3.4.8 Ophthalmologist

The ophthalmologist will review and interpret the ophthalmological examinations and optical coherence tomography (OCT)¹ assessments as scheduled in the study protocol [see Section 7.5.7 and 7.5.8]. In the event of suspected clinically significant findings (e.g., macular edema or active uveitis), an unscheduled OCT examination should be performed by the ophthalmologist, and the principal investigator / treating neurologist will be notified for reporting of an AE on the AE page of the eCRF. In the event of findings observed at any visit during the study, the ophthalmologist

-

Scheduled OCT assessments are only applicable to Global Protocol version 1 to 5. The requirement for scheduled OCT assessments was removed from Protocol Version 6 onwards.

15 March 2022, page 58/216

EudraCT 2016-004719-10 EDMS-ERI-207656619

Confidential

will conduct further examination, as per local standard practice, to rule out or confirm the diagnosis.

3.4.9 Pulmonary function laboratory technician or expert

The PFTs must be performed by experienced staff, such as a pulmonary function technician or expert, according to the American Thoracic Society / European Respiratory Society (ATS/ERS) guidelines [Miller 2005a].

3.4.10 Pulmonologist

At sites participating in the DL_{CO} sub-study, a pulmonologist or a physician adequately trained in respiratory medicine will review DL_{CO} results. If clinically significant alterations in DL_{CO} variables indicating a pulmonary condition that could result in increased risk for the subject are observed, she/he may be prematurely discontinued from the study treatment at the discretion of the principal investigator / treating neurologist. Significant findings, which in view of the pulmonologist meet the definition of an AE, must be reported to the principal investigator / treating neurologist and recorded on the AE page of the eCRF. In the event of findings observed at any visit during the study, the pulmonologist will conduct further examination, as per local standard practice, to rule out or confirm the diagnosis.

3.4.11 Dermatologist

A dermatologist will perform a complete skin examination as indicated in Table 1 and Table 2.

Significant findings, which in view of the dermatologist meet the definition of an AE, must be reported to the principal investigator / treating neurologist and recorded on the AE page of the eCRF. In the event of findings observed at any visit during the study, the dermatologist will conduct further examinations, as per local standard practice, to rule out or confirm the diagnosis.

3.5 Study committees

3.5.1 Independent Data Monitoring Committee

The Independent Data Monitoring Committee (IDMC) responsible for monitoring the core study has continued its duties for the extension study, until its disbandment which occurred on 30th September 2021. It was composed of physicians with relevant medical expertise. The composition and operation of the IDMC was described in the IDMC charter.

3.5.1.1 Independent Statistical Analysis Center

An independent Statistical Analysis Center (ISAC, Frontier Science), not otherwise involved in study conduct or statistical analysis, will generate all analysis reports required throughout the trial period, exclusively for review by the IDMC (including if required unblinded analysis by treatment allocation in the core study). The reports will be generated from efficacy and safety data periodically transferred by the sponsor to the ISAC.

15 March 2022, page 59/216

Confidential

EudraCT 2016-004719-10 EDMS-ERI-207656619

3.5.2 Ophthalmology Safety Board

An Ophthalmology Safety Board (OSB) composed of two independent ophthalmologists will review and evaluate any new or suspected cases of macular edema. The composition and operation of the OSB is described in the OSB charter. From Protocol Version 6 onwards, the OSB will be decommissioned as macular edema is considered a well characterized identified risk with treatment with ponesimod.

3.5.3 Major adverse cardiovascular events adjudication board

A major adverse cardiovascular events (MACE) adjudication board will review and evaluate the MACE reported in the study. The selection of AEs that will be sent for adjudication will be based on a pre-defined list of preferred terms belonging to relevant Standardized MedDRA Queries. For each AE sent for MACE adjudication, the MACE adjudication board will determine whether the event belongs or does not belong to one of the pre-specified categories, including cardiovascular death, myocardial infarction, or stroke.

The composition and operations of MACE adjudication board will be described in the MACE adjudication board charter.

4 SUBJECT POPULATION

4.1 Subject population description

This study will enroll adult male and female subjects who have completed the 108-week treatment period in the core study. These subjects were determined to have an established diagnosis of MS, as defined by the 2010 revision of McDonald Diagnostic Criteria [Polman 2011], with relapsing course from onset (i.e., RRMS and SPMS with superimposed relapses).

4.2 Inclusion criteria

- 1. Signed informed consent, prior to initiation of any study-mandated procedure.
- 2. Subjects with MS having completed the double-blind treatment in the core study as scheduled (i.e., who completed the double-blind treatment period until Week 108).
- 3. Compliance with the teriflunomide elimination procedure assessed as sufficient by the investigator at visit FU1 or abbreviated visit FU2 of the core study, whichever occurred last (the recommended compliance should include intake of 33 doses of cholestyramine (8 g or 4 g) or 22 doses of activated charcoal (50 g).
- 4. For subjects of reproductive potential: #
 - Women of childbearing potential (WOCBP):
 - Must have a negative pre-treatment urine pregnancy test on Day 1;
 - Must agree to undertake 4-weekly urine pregnancy tests during the study and until 6 weeks after the first of two consecutive tests showing teriflunomide plasma level <0.02 mg/L and until at least 30 days after study treatment discontinuation;
 - Must have been using reliable methods of contraception uninterrupted since EOT in the core study and must agree to continue using reliable methods of contraception

EudraCT 2016-004719-10 EDMS-ERI-207656619

Confidential

15 March 2022, page 60/216

throughout the study until 6 weeks after the first of two consecutive tests showing teriflunomide plasma level <0.02 mg/L and until at least 30 days after discontinuation of study treatment.

• Fertile male subjects participating in the study who are sexually active with WOCBP must agree to use a condom until 6 weeks after the first of two consecutive tests confirming plasma teriflunomide level <0.02 mg/L.

Definition of WOCBP, fertile male subjects and the acceptable methods of contraception for this study are described in Section 4.4.

Women who interrupt the study treatment because of planned pregnancy will be exempt from any protocol-mandated pregnancy tests after the first positive urine pregnancy test and until 30 days before study drug re-initiation. These women will also interrupt contraception 30 days after the study treatment interruption and until after delivery [see Section 5.1.12.4].

The inclusion criterion 4 was valid for all subjects throughout the recruitment period. Following approval of protocol version 5 (by which time all subjects had been off teriflunomide for over 2 years), teriflunomide plasma testing is no longer required.

4.3 Exclusion criteria

- 1. Any of the following cardiovascular conditions on Day 1 pre-dose:
 - a. Resting heart rate (HR) <50 beats per minute (bpm) as measured by the pre-dose 12-lead ECG;
 - b. Presence of second or third degree atrioventricular (AV) block or a QT interval corrected for heart rate on the basis of Fridericia's formula (QTcF) >470 ms (females), >450 ms (males) on pre-dose 12-lead ECG.
- 2. Any of the following alerts from central laboratory at Visit 14 of the core study (EOT) which was confirmed as an alert at repeated testing or not repeated prior to FU1 of the core study:
 - a. Lymphocyte count: $<0.2 \times 10^9/L$ ($<200/mm^3$ blinded results):
 - b. Neutrophil count $<1.0 \times 10^9/L$ ($<1000 \text{ cells/mm}^3$);
 - c. Platelet count $<50 \times 10^9/L$ (<50~000 cells/mm³);
 - d. Creatinine clearance <30 mL/min (Cockroft-Gault).
- 3. At Visit 14 of the core study (EOT) >30% decrease from core study baseline FEV₁ and/or forced vital capacity (FVC);
- 4. Clinically significant, persistent respiratory AEs (e.g., dyspnea) not resolved prior to first dosing in the extension study.
- 5. Macular edema at any time between Visit 1 (Screening) in the core study and Day 1 of extension study.
- 6. Presence of the following at core study Visit 14 (EOT, Week 108), FU1, or abbreviated visit FU2, or on Day 1 (pre-dose) of the extension study:

15 March 2022, page 61/216

Confidential

EudraCT 2016-004719-10 EDMS-ERI-207656619

- a. Suspected opportunistic infection of the CNS or any other infection which, in the opinion of the investigator, contraindicates re-start of the study drug;
- b. Stevens-Johnson syndrome or toxic epidermal necrolysis or drug reaction with eosinophilia and systemic symptoms.
- 7. Need for and intention to administer forbidden study-treatment-concomitant therapy;
- 8. Women who are pregnant or lactating;
- 9. Male subjects wishing to father a child any time before the 6 week period following the first of two consecutive tests confirming plasma teriflunomide level <0.02 mg/L;
- 10. Treatment with any MS DMTs between core study EOT and first dosing in extension study;
- 11. Any other clinically relevant medical or surgical condition, which, in the opinion of the investigator, would put the subject at risk by participating in the study;
- 12. Subjects unlikely to comply with protocol, e.g., uncooperative attitude, inability to return for follow-up visits, or known likelihood of not completing the study including mental condition rendering the subject unable to understand the nature, scope, and possible consequences of the study.

4.4 Subjects of reproductive potential

WOCBP and fertile male subjects participating in the study must agree that they will take means to reduce reproductivity risk as defined in the following sections.

4.4.1 Women of childbearing potential

A woman is considered to be of childbearing potential unless she meets at least one of the following criteria:

- Previous bilateral salpingo-oophorectomy or hysterectomy.
- Premature ovarian failure confirmed by a specialist.
- XY genotype, Turner syndrome, uterine agenesis.
- Postmenopausal, defined as 12 consecutive months with no menses without an alternative medical cause (ICH M3 definition).

WOCBP participating in the study must have been using one of the following reliable methods of contraception uninterrupted since EOT in the core study, and must agree to continue using these methods of contraception treatment until 6 weeks after the first of two consecutive tests showing teriflunomide plasma level <0.02 mg/L and until at least 30 days after discontinuation of study treatment:

- Two methods of contraception, one from Group 1 and one from Group 2, defined as follows:
 - Group 1: Oral, implantable, transdermal or injectable hormonal contraceptives or intrauterine devices. If a hormonal contraceptive is chosen from this group, it must be taken for at least 30 days prior to enrollment.
 - Group 2: Female or male condoms, diaphragm or cervical cap.

15 March 2022, page 62/216

Confidential

EudraCT 2016-004719-10 EDMS-ERI-207656619

• True abstinence from intercourse with a male partner only when this is in line with the preferred lifestyle of the subject.

OR

• Permanent female sterilization (tubal occlusion/ligation at least 6 weeks prior to enrollment).

OR

• Sterilization of the male partner with documented post-vasectomy confirmation of the absence of sperm in the ejaculate.

Rhythm methods or the use of a condom by a male partner alone are not considered acceptable methods of contraception for this study.

The methods of contraception used (including non-pharmacological methods) must be recorded in the eCRF.

4.4.2 Fertile male subject

A fertile male is defined as physiologically capable of conceiving offspring.

Fertile male subjects participating in the study who are sexually active with WOCBP must agree to use a condom for up to 6 weeks after the first of two tests showing teriflunomide plasma level <0.02 mg/L[#] and not to father a child during this period. Female partners of fertile male subjects, if WOCBP, will need to use effective methods of contraception[#] [Aubagio[®] USPI, Aubagio[®] SmPC], as recommended by the investigator during the same period.

Important note: Teriflunomide testing is no longer required with the approval of protocol version 5. In consequence, there are no longer any restrictions with regards to male subjects who intend to have a child.

4.5 Medical history

4.5.1 Ongoing medical history from the core study

Clinically significant past or concomitant disease or diagnosis ongoing from the core study and ongoing at enrollment of the extension study is collected in the extension study eCRF prior to enrollment.

4.5.2 Additional medical history not reported in the core study

Any new or additional clinically significant past or concomitant disease or diagnosis that cannot be reported in the core study database is collected in the extension study eCRF prior to enrollment.

4.5.3 MS disease history

Complications or symptoms associated with MS present within 24 months prior to the core study and ongoing at enrollment of the extension study are collected in the extension study eCRF prior to enrollment.

Confidential

EudraCT 2016-004719-10 EDMS-ERI-207656619

4.5.4 MS disease changes

15 March 2022, page 63/216

Any MS disease (e.g., RRMS or SPMS with superimposed relapses) changes since the subject entered the core study are collected in the extension study eCRF prior to enrollment.

5 TREATMENTS

5.1 Study treatment

The study treatment is the investigational drug ponesimod. The treatment period consists of an uptitration period (from Day 1 to 14) and a maintenance period (Day 15 until EOT). Ponesimod dose is increased over 15 days until a maintenance dose of 20 mg is reached.

Note that the term "study treatment" or "study drug" refers to study medication provided by the sponsor, as opposed to "commercially available ponesimod" that may be started after discontinuation of study treatment.

5.1.1 Investigational treatment: description and rationale

Ponesimod is supplied as its free base, in oral film-coated tablets at the doses of 2, 3, 4, 5, 6, 7, 8, 9, 10, and 20 mg. One tablet of ponesimod 2, 3, 4, 5, 6, 7, 8, 9, or 10 mg will be taken orally o.d. during the up-titration period (Day 1 to 14). During the maintenance period, one tablet of ponesimod 20 mg will be taken orally o.d.

5.1.2 Study treatment administration

5.1.2.1 Up-titration (performed by IVRS)

A gradual up-titration of ponesimod from a 2 mg starting dose to a 20 mg maintenance dose over a period of 14 days was found to successfully mitigate first-dose effects. This 2 week up-titration regimen will be implemented in the study on initiation of treatment (Day 1) and on days of reinitiation of treatment following treatment interruption of 4 days or more [see Section 5.1.9].

Confidential

Table 3 Dosing scheme

15 March 2022, page 64/216

Version 6

Treatment period	Duration	Dose regimen	Dose level
Up-titration	Day 1 and 2	2 mg	1 and 2
Up-titration	Day 3 and 4	3 mg	3 and 4
Up-titration	Day 5 and 6	4 mg	5 and 6
Up-titration	Day 7	5 mg	7
Up-titration	Day 8	6 mg	8
Up-titration	Day 9	7 mg	9
Up-titration	Day 10	8 mg	10
Up-titration	Day 11	9 mg	11
Up-titration	Day 12 to 14*	10 mg	12 to 14
Maintenance	Day 15 until EOT	20 mg	15 to 17*

^{* =} Visit 2 is to take place at Day 15 (1 / +3 day). The titration kit will therefore include 3 additional tablets (to be used if applicable) for treatment on Day 15-17 (i.e., dose regimen = 20 mg).

EOT = End-of-Treatment.

Study treatment up-titration, other than described above, is prohibited. Study treatment down titration is not foreseen in any situation and is prohibited.

One tablet will be taken orally o.d., preferably in the morning, either with breakfast or before or after breakfast, at approximately the same time each day. The tablet will be swallowed as a whole. The last administration date and time of study treatment prior to the study visits and the administration date and time of study treatment on the days of visits will be recorded in the eCRF.

5.1.2.2 Maintenance

One tablet of ponesimod will be taken orally o.d., preferably in the morning, either with breakfast or before or after breakfast. It is preferable that the tablet be taken each day at approximately the same time. The tablet will be swallowed whole. The last administration date and time of study treatment prior to the study visits and the administration date and time of study treatment on the days of visits will be recorded in the eCRF.

On the day of the study visits, study treatment must be administered only after the completion of the pre-dose safety assessments (diastolic and systolic blood pressure [DBP/SBP], ECGs, PFTs, laboratory tests).

5.1.3 Treatment assignment

After the subject has signed the informed consent form and eligibility has been confirmed, the investigator/delegate contacts the Interactive Response Technology system (IRT) at Visit 1 to enroll the subject.

Confidential

EudraCT 2016-004719-10 EDMS-ERI-207656619

5.1.4 Blinding

15 March 2022, page 65/216

The treatment groups in the core study remained blinded until the randomization list was revealed for the core study.

5.1.5 Study treatment supply

Manufacturing, labeling, packaging, and supply of study treatment will be conducted according to Good Manufacturing Practice (GMP), Good Clinical Practice (GCP), and any local or national regulatory requirements.

All study treatment supplies are to be used only in accordance with this protocol, and not for any other purpose.

5.1.5.1 Study treatment packaging and labeling

5.1.5.1.1 Study treatment packaging

Study treatment is provided as tablets and supplied in blister packs or bottles.

5.1.5.1.2 Study treatment labeling

Study treatment is labeled to comply with the applicable laws and regulations of the countries in which the study sites are located.

5.1.5.2 Study treatment distribution and storage

Treatment supplies must be kept in an appropriate, secure area, and stored according to the conditions specified on the medication labels.

5.1.5.3 Study treatment dispensing

The subjects will receive sufficient study treatment to cover the period up to the next scheduled visit. Alternatively, scheduled study medication dispensing/return procedures may be adapted according to the site practice (i.e., if the subject comes to the investigational site more frequently than the scheduled visits, it is then possible to dispense medication in smaller quantities). Subjects are asked to return all used, partially used and unused study treatment blister packs/bottles at each visit. If the subject forgets to bring the remaining study treatment to a study visit, she/he must be instructed not to take any tablets from the remaining study treatment, and to bring the remaining study treatment to the next visit.

An accurate record of the date and amount of study treatment dispensed to each subject must be available for inspection at any time.

5.1.5.4 Study treatment return and destruction

On an ongoing basis and/or on termination of the study, the monitor will collect used and unused subject kits. The return to the sponsor of unused study drug, or used returned study drug for destruction, will be documented on the investigational product destruction form. When the study

15 March 2022, page 66/216

Confidential

EudraCT 2016-004719-10 EDMS-ERI-207656619

site is an authorized destruction unit and study intervention supplies are destroyed on-site, this must also be documented on the investigational product destruction form.

5.1.6 Study treatment accountability and compliance with study treatment

5.1.6.1 Study treatment accountability

The inventory of study treatment dispensed and returned (i.e., study treatment accountability) must be performed by the study staff on the day of the subject visit and before providing further study treatment. It is recorded on the IMP dispensing and accountability log as well as in the eCRF, and checked by the Clinical Research Associate (CRA) during site visits and at the end of the study. The study treatment accountability log in the eCRF will include at least the following information for each study treatment unit dispensed to the subject:

- Dispensed kit number
- Date dispensed / Number of tablets dispensed.
- Date returned / Number of tablets returned.

All study treatment supplies, including partially used or empty blisters/bottles must be retained at the site for review by the CRA.

If the subject forgets to bring the remaining study treatment to a study visit, he/she must be instructed to not take any tablet from the remaining study treatment and to bring it at the next visit.

5.1.6.2 Study treatment compliance

Study treatment compliance is based on study treatment accountability. Study treatment compliance will be calculated at each visit using the formula defined below:

Compliance =

[(number of tablets dispensed – number of tablets returned) / total number of tablets that should have been taken during the period*] \times 100

* The period is defined as the number of days between visits and is equal to the number of tablets that should have been taken.

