5.1.8 Study treatment dose adjustments and interruptions

Study treatment up-titration, other than described in Section 5.1.2, is prohibited. Study treatment down-titration is not foreseen in any situation and is prohibited.

Study treatment interruption should be avoided. If study treatment intake is interrupted by the subject for any reason, she/he must immediately inform the investigator / treating neurologist.

Study treatment may be temporarily interrupted in response to an AE, a diagnostic or therapeutic procedure, a laboratory abnormality, vaccination (see Section 5.2.3), or for administrative reasons. Study-specific criteria for interruption of study treatment are described in Section 5.1.12. The permitted maximum duration of the study treatment interruption is 81 weeks for planned pregnancies and 12 weeks for other reasons (if exceeded, the subject will then be prematurely discontinued from the study).

Detailed guidance on how to re-initiate study treatment in the event of drug interruption is provided in Section 5.1.9.

Study treatment dose interruptions must be recorded in the eCRF.

5.1.9 Guidance for re-initiation of study treatment in the event of study treatment interruption

If study treatment intake (up-titration or maintenance phases) is interrupted by the subject for any reason, she/he must immediately inform the principal investigator / treating neurologist.

The following guidance is provided for re-initiation of investigational study treatment after study treatment interruptions.

A schematic overview of the re-initiation algorithm is given below in Figure 2.

Depending on the day, time, and duration of study treatment interruption, the following procedures will be followed.

- If the subject missed taking the dose in the morning:
 - The dose should be taken at any time on the same day.
 - Regular dosing should be resumed with the morning dose on the following day.
- If the subject missed taking the dose for up to three consecutive days:
 - Dosing should be resumed in the morning, with the same dose taken prior to study treatment interruption.
 - Study treatment intake may be re-initiated by the subject at home.

15 March 2022, page 68/216

Confidential

- Subjects must be instructed to contact the investigator immediately if they experience any symptoms of bradycardia (e.g., dizziness, vertigo, syncope).

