- The need for re-uptitration at the study treatment re-initiation.
- Breastfeeding must be completely stopped prior to the re-initiation of the study treatment.
- The need to follow the visit schedule as per protocol during pregnancy, including all scheduled assessments and procedures except MRI, PFTs, and without study treatment dispensing.

The re-start of study treatment after delivery requires the following eligibility criteria to be met:

- The subject has completely stopped breastfeeding prior to re-start of the study treatment.
- The subject must have been using the reliable methods of contraception as described in Section 4.4.1 for at least 30 days prior to re-start of study treatment.
- The subject must have had 2 negative urine pregnancy tests performed 30 days apart; the second one must be during the re-start visit.
- The subject did/does not fulfill any protocol criteria for permanent study treatment discontinuation [see Section 5.1.12] at any of the previous visits or at the unscheduled visit for re-start of the study treatment, except the planned pregnancy.
- If the subject received another DMT (IFN β or glatiramer acetate) during pregnancy and post-partum, this treatment must be discontinued at least 7 days before study treatment re-start.

If the subject agrees to all of the above, the study treatment will be interrupted at the scheduled visit once the subject, after having received the above explanation from the principal investigator / treating neurologist, has confirmed the wish to become pregnant and interrupt and potentially restart the study treatment. The sponsor must be contacted in each particular case in order to confirm that the subject who wishes to become pregnant can continue in the study.

The above requirements for re-initiation of study drug after delivery apply to all cases of study treatment interruption for planned pregnancy irrespective of the duration of pregnancy, and also

EudraCT 2016-004719-10 EDMS-ERI-207656619

Confidential

to all cases where planned pregnancy did not occur but where contraception was interrupted for any duration, and the subject thereafter wishes to re-start study treatment.

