5.2.3 Forbidden study-treatment-concomitant therapy

- Systemic corticosteroids and ACTH, except for the treatment of MS relapses [see Section 5.2.1] and for short-term treatment (up to 2 weeks per treatment cycle with at least 8 weeks' interval between treatment cycles and no more than 4 weeks per year of the study duration on average) with low dose of corticosteroid (up to 10 mg of prednisone equivalent daily) or inhaled corticosteroids for pulmonary conditions;
- Disease-modifying drugs for MS other than prescribed as per protocol (except glatiramer acetate or INF β-1a during ponesimod interruptions for planned pregnancy as described under "Allowed").
- Immunosuppressive treatment (e.g., cladribine, lymphocyte-depleting biological agents such as rituximab or ocrelizumab, mitoxantrone, or other systemic immunosuppressive treatments such as azathioprine, cyclophosphamide, cyclosporine or methotrexate);
- i.v. immunoglobulin (except in women who have interrupted study treatment for pregnancy; for these women i.v. immunoglobulin will be allowed after 30 days from interruption of the study treatment);
- Plasmapheresis, cytapheresis, or total lymphoid irradiation;
- Vaccination with live vaccines, except if performed during a temporary treatment interruption
 period. In this case it must be performed not earlier than 1 week after last dose of study
 treatment, and treatment can be re-initiated only after at least 4 weeks from completion of
 vaccination;
- β-blockers, diltiazem, verapamil, digoxin, digitoxin or any other anti-arrhythmic or HR lowering systemic therapy (a non-exhaustive list of drugs provided in Appendix 3) during the up-titration period (i.e., from Day 1 until Day 14 included, and during the first 14 days after re-initiation of study treatment). Treatment with any of these therapies is also not recommended during the maintenance treatment period (from Day 15 until EOT) and should be considered with caution if an alternative medication cannot be used;

Confidential

EudraCT 2016-004719-10 EDMS-ERI-207656619

Any other investigational drug;

15 March 2022, page 84/216

• Any investigational therapeutic procedure for MS (e.g., stent placement or angioplasty for chronic cerebrospinal venous insufficiency, stem-cell transplantation).

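### The compliance denominator counts protocol-permitted interruption days as tablets that should have been taken, so a fully adherent subject can score as low as 0%

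*Protocol*

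**What the plan says.** Section 5.1.6.2 states that "Study treatment compliance will be calculated at each visit using the formula defined below". The formula is ("number of tablets dispensed – number of tablets returned) / total number of tablets that should have been taken during the period") × 100, and the footnote adds: "The period is defined as the number of days between visits and is equal to the number of tablets" that should have been taken. Nothing is deducted for days off treatment.

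Other sections create such days:

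- Section 5.1.8 sets limits: the maximum permitted "study treatment interruption is 81 weeks for planned pregnancies and 12 weeks for other reasons". It also requires interruptions to be recorded in the eCRF.
- Section 3.2.3 keeps subjects on the planned visit schedule while off treatment.
- Section 5.1.12.5 keeps the visit schedule running during planned pregnancy, "except MRI, PFTs, and without study treatment dispensing".
- Section 5.2.3 allows live vaccination only in an interruption: at least 1 week after the last dose, and then "treatment can be re-initiated only after at least 4 weeks from completion of" the vaccination.

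On returns, Section 5.1.6.1 foresees the case: "If the subject forgets to bring the remaining study treatment to a study visit", the subject leaves those tablets untouched and brings them to the following visit. Section 5.1.6.2 does not say how compliance is computed in the meantime.

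**The concern.** The footnote treats calendar days and tablets due as the same number. On a day when the protocol permits or requires the subject to be off treatment, the tablets due are zero, yet the denominator still adds one. The result merges two different things: doses missed against instructions and doses withheld in line with them. The study has an objective on re-initiation after interruption (Section 2.1), so the two should stay apart.

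The figure is also used during conduct. Sections 8.3.2 to 8.3.10 list a compliance review at the treatment visits, so sites would see low values for subjects who did nothing wrong. Conversely, at a visit where leftovers are absent, the figure can read 100% or more although doses were missed.

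**Working it through.** The protocol gives no compliance value to reproduce, so the formula is applied as written: C = 100 × (dispensed − returned) / days between visits.

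**Control.** Table 3 in Section 5.1.2.1 gives a titration kit of 14 daily tablets plus 3 spares, 17 in all. With 14 taken and 3 returned over 14 days, C = (17 − 3)/14 = 100.0%. The formula works when everything is returned and nothing is interrupted.

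**Interruption days.** Inputs: a 12-week interval of 84 days (Section 3.2.3), visits on schedule, a subject who takes every tablet that is due, unused tablets returned at the visit, and no re-initiation visit inside the interval.

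| Days off in 84 | As written | With days off subtracted |
|---|---|---|
| 14 | 70/84 = 83.3% | 70/70 = 100% |
| 35 (live vaccine minimum, 7 + 28) | 49/84 = 58.3% | 49/49 = 100% |
| 84 (12-week maximum) | 0/84 = 0% | 0/0, not applicable |

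Planned pregnancy: 81/12 = 6.75 intervals. If the interruption starts at a scheduled visit, six whole intervals read 0%. The seventh has 9 of 12 weeks off and reads 21/84 = 25%, if unsplit.

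**Effect of a re-initiation visit.** Section 8.5.3 puts a visit on the day of re-initiation after four or more missed days, and Table 2 marks dispensing and accountability there. Suppose the 35 days off begin at a scheduled visit and that visit falls at their end. The first part then reads 0/35 = 0% and the second 49/49 = 100%. If the subject first takes 14 tablets, the first part reads 14/49 = 28.6% and the second 35/35 = 100%. The split moves the shortfall into a shorter interval; it does not remove it.

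**Forgotten tablets.** A fully adherent subject who leaves the 3 spare titration tablets at home reads 17/14 = 121.4%. In an 84-day interval with 84 dispensed, 8 doses missed and the leftovers forgotten, the visit reads 84/84 = 100% (true 76/84 = 90.5%). If the 8 are then counted at the next visit after a perfect interval, that visit reads (84 − 8)/84 = 90.5% (true 100%). Over both intervals, (84 + 76)/168 = 95.2%, which is correct. If the 8 never come back, the two-interval figure is 168/168 = 100%.

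The pack size is not given. If 7, 14 or 28 surplus tablets were dispensed per interval (assumed range), the first visit would read 91/84 = 108.3%, 98/84 = 116.7% or 112/84 = 133.3%.

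**The case against.** The strongest reply is that little depends on this figure. Compliance is not among the endpoints in Section 6. Section 11.4.2.2 runs the main relapse-rate analysis regardless of compliance. Section 11 leaves derivation algorithms to the SAP, which is not shown and may define an analysed compliance variable differently. All of this stands, and it limits the weight of the point. It does not remove it: Section 5.1.6.2 does not defer the denominator but fixes it, and the formula serves the review at treatment visits, which a later SAP definition would not change.

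The reply on forgotten tablets is also largely right. The accountability log is kept per dispensed unit with dates and counts of dispensing and return (Section 5.1.6.1), so late returns can be reconciled, and charging them to the later interval is only one reading of the text. The error cancels over time unless tablets never come back, which is a limit of any pill count.

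The single-interval figures of 83.3% and 58.3% do assume that no re-initiation visit splits the interval. The split changes the numbers, not the conclusion.

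A reader might go further in three ways that the protocol does not support:

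- That compliance is the only record of dose delivered. Interruptions (Section 5.1.8) and the dates and times of the last dose before visits and of dosing on visit days (Sections 5.1.2.1 and 5.1.2.2) are also recorded.
- That the Per-Protocol Set would be misclassified. Section 11.2.4 rests on major deviations to be defined in the SAP, and the protocol states no compliance threshold.
- That compliance over the whole study would be understated, for instance (240 − 81)/240 = 66.3%. The protocol defines compliance per visit and specifies no whole-study figure.

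**Conclusion.** The point holds for the denominator. Section 5.1.6.2 equates days between visits with tablets due, and the protocol's own interruption rules make that untrue. A fully adherent subject reads anything from slightly under 100% down to 0% for an interval, and the shortfall is never recovered at a later visit. The forgotten-tablet problem is real but secondary: a per-visit distortion that cancels if the tablets return.

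The impact is minor, confined to the descriptive and per-visit compliance figure. Any effect on analysis sets would depend on SAP rules that are not shown. The sizes assume on-schedule visits and unused tablets returned; the number of subjects affected cannot be derived from the protocol. The interruption rules themselves are not in question.

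**What to change.** Amend the Section 5.1.6.2 footnote along these lines:

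- Denominator: days between visits minus protocol-permitted interruption days recorded in the eCRF.
- Where no dosing day remains, report compliance as not applicable, not 0%.
- Report interruption days separately, next to the compliance figure.
- Credit late-returned tablets to the kit and interval in which they were dispensed, and flag that interval as provisional until the kit is back.

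The cost is one formula and its programming; the kit-level log and the interruption record already exist. There are two small downsides. Interval compliance stays provisional until kits return, so kits never returned need a stated rule. The interruption record must also identify which interruptions were permitted: Section 5.1.8 requires interruptions to be recorded but does not say that the reason is captured, and it allows administrative reasons. Separate reporting of the days removed guards against the subtraction hiding avoidable gaps.
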